5.3 Study Duration

Individual subjects will be in the study for a total of 90 days. They will receive a telephone call at 48 hours and either a computer based or telephone based interview at 30+/- 3 days and then will have an in-person visit at 90+/-7 days.

Total study duration is expected to last approximately 2 years. We expect to enroll about 6 subjects per month and should reach our target of 90 patients by 15 months. The final follow-up visit will occur 3 months after the last patient is enrolled. Data collection and analysis will be completed in the subsequent 6 months for total study duration of 24 months.

6. DRUGS OR DEVICES

All patients will receive a Withings wireless blood pressure monitor. This commercially available device measures heart rate and blood pressure. The device is operated by and communicates with both Apple and Android smart phones (Apple iPhone 3GS and newer, Android 4.0 and newer) via bluetooth. Blood pressure and heart rate readings will be automatically uploaded to Penn’s *Way to Health* platform via the subject’s smart phone. There are no risks associated with this device. All subjects will be instructed on the proper use of the device as well as best practices for measuring blood pressure at the time of study enrollment.

Way to Health is an integrated research platform that uses online tools to connect with and collect data from wireless devices. Blood pressure and heart rate data will be collected and stored in a secure, HIPAA compliant format. The platform will provide automatic reminders for all patients to use the blood pressure cuff twice daily. Additionally, the platform will automatically apply the social incentive to randomized subjects. The social incentive is described in more detail later (section 7.1).

7. STUDY PROCEDURES

7.1 ENROLLMENT

At the time of enrollment the following data will be collected: Age, sex, race, ethnicity, handedness (left arm dominate, right arm dominate), date of stroke, etiology of stroke (large vessel disease, small vessel disease, cardioembolic, other defined etiology, cryptogenic), past medical history (including prior history of: hypertension, diabetes, hyperlipidemia, atrial fibrillation, congestive heart failure, coronary artery disease and/or myocardial infarction, chronic kidney disease, peripheral artery disease, stroke prior to the enrolling event, and other), current medications, smoking history (current, former, never smoker), employment status (currently employed, disabled, retired), living situation (lives alone yes/no, if no, number of people and relationship of people living in the home), annual household income (<\$20,000, \$20,000-39,999, \$40,000-64,999, \$65,000-104,999, \$105,000+), insurance status (private health insurance, medicare, medicaid, none), primary care provider (yes/no), cardiologist (yes/no), nephrologist (yes/no). We will also obtain contact information for follow-up phone calls and for scheduling the 90 day visit. Social security numbers will be collected for subject reimbursement purposes.

Figure 1. Modified Rankin Scale

Modified Rankin Scale	
0	No symptoms
1	No disability; able to carry out all previous activities despite some symptoms
2	Slight disability; unable to carry out all previous activities but able to look after own affairs
3	Moderate disability; requires some help but able to walk unassisted
4	Moderately severe disability; unable to attend to own bodily needs and unable to walk unassisted.
5	Severe disability; requires constant nursing care and attention, bedridden.

Study Measurements at enrollment

- Upper arm circumference. Measured using a tape measure in the mid-portion of the upper arm. Circumference <9" or >17" is an exclusion criteria.
- Mini-Mental Status Examination (MMSE) – the MMSE is a brief, standardized cognitive assessment. Subjects will be excluded if they score ≤ 20 on the MMSE, which corresponds to moderate or severe dementia.

2. Modified Rankin Scale (mRS). The mRS is a 5 point scale which ranges from no disability to severe disability (figure 1). It is assessed using a brief, structured interview. Study personnel will be trained and certified in the use of the mRS. Subjects with mRS >2 are excluded.

3. National Institute of Health Stroke Scale (NIHSS). The NIHSS is a brief, structured neurologic examination, designed to assess deficits from stroke (figure 2). Study personnel will be trained and certified in the use of the NIHSS.

4. Heart Rate and blood pressure – Heart rate and blood pressure will be measured at least 30 minutes after exercise. The patient will have been sitting for at least 5 minutes before blood pressure is checked. The patient will be asked to sit in a chair with their back straight and supported and their feet flat on the floor. The arm will be supported on a flat surface at approximately the level of the heart. Blood pressure and heart rate will be assessed in the non-dominant arm using an

NIH Stroke Scale	
1a. LOC 0 alert 1 drowsy 2 stuporous 3 coma	6. Motor Leg a. Left Leg 0 no drift 1 drift 2 cannot resist gravity 3 no effort against gravity 4 no movement
1b. LOC ?'s 0 both correct	
Figure 2. NIH Stroke Scale	
1c. LOC Commands 0 both correct 1 one correct 2 incorrect	7. High Leg 0 no drift 1 drift 2 cannot resist gravity 3 no effort against gravity 4 no movement z amputation/joint fusion
2. Best Gaze 0 normal 1 partial gaze palsy 2 forced deviation	8. Limb Ataxia 0 absent 1 present in one limb 2 present in two limbs
3. Visual Fields 0 no visual loss 1 partial hemianopsia 2 complete hemianopsia 3 bilateral hemianopsia	9. Sensation 0 normal 1 partial loss 2 severe loss
4. Facial Palsy 0 normal 1 minor 2 partial central 3 complete	10. Best Language 0 no aphasia 1 mild-mod aphasia 2 severe aphasia 3 mute
5. Motor Arm a. Left Arm 0 no drift 1 drift 2 cannot resist gravity 3 no effort against gravity 4 no movement z amputation/joint fusion	11. Dysarthria 0 none 1 mild-mod 2 severe/mute z intubated
b. Left Arm 0 no drift 1 drift 2 cannot resist gravity 3 no effort against gravity 4 no movement z amputation/joint fusion	11. Extinction 0 no neglect 1 partial neglect 2 complete neglect
Total Score	

automated sphygmomanometer. This will be repeated for a total of three measurements, which will be averaged to determine the baseline blood pressure.

Education

At the time of enrollment, the patient will receive general education about hypertension, including proper technique for blood pressure measurement, goal blood pressure, and appropriate actions to take if blood pressure is severely elevated or abnormally low. Additionally patients will be educated on the proper use of the Withings Blood Pressure monitor. The appropriate software will be downloaded onto their smart phone and they will be supervised as they measure their own blood pressure with the device. Subjects will be encouraged to measure blood pressure in their non-dominant arm for ease of monitor placement. Subjects will be instructed to take their BP prior to or at least 2 hours after moderate or high intensity exercise. Subjects will be instructed to take their BP twice daily, once between 6:00am-11:59am and once between 4:00pm-9:59pm. Finally, patients will be enrolled onto the Way to Health platform and will choose whether they prefer to receive study communications via email or text message. The subject will also be given a telephone number that they may call if they encounter any technical difficulties with the Withings device.

Connected Health Monitoring

The Withings blood pressure cuff provides the subject with a graphical display of their blood pressure after it is measured as well as prior blood pressure readings. Blood pressure readings are color coded to indicate Normal blood pressure, mild, moderate, and severe hypertension. BP readings will be automatically uploaded from the subject's device to Way to Health. If subjects have not completed their morning BP check by 11:00am they will receive a reminder via their chosen form of communication (email or text). In the evening they will receive a reminder if they have not checked their BP by 9:00pm. In addition to the standard feedback provided within the Withings app, subjects will receive automated feedback from the Way to Health platform on a weekly basis. This message will contain the subject's mean blood pressure over the preceding 7 days. This message will also note whether the subject's blood pressure is above or below a goal of <140/90 mm Hg and will report their compliance with scheduled BP checks.

Social Incentive

Patients will be randomly assigned (1:1) to either receive a social incentive or not. The social incentive will require the subject to identify a social supporter. This individual can be a family member, friend, or other community member selected by the subject. The social supporter will need to assent to the study and register on the Way to Health platform. The social supporter will receive education on the importance of hypertension, how to measure blood pressure, and how to operate the Withings monitor. If the social supporter is not present at the time of subject enrollment, they may assent to the study via telephone and/or by registering online at the Way to Health platform. In this scenario they will receive education via telephone and/or online.

The social supporter will choose whether they prefer to receive study communications via text message or email. The social supporter will receive a text or email message alert at 11:00am if the subject has not completed their morning BP reading and at 9:00pm if the subject has not completed their evening BP reading. The social supporter will also receive feedback on the subject's BP control from the Way to Health platform on a weekly basis. This message will summarize the subject's adherence to home monitoring in the preceding 7 days. It will also contain the subject's mean BP over the preceding 7 days and note whether the subject's BP is above or below a goal of <140/90 mm Hg. The expectation is that the social support person will provide further feedback to the subject in order to improve both adherence and BP control.

Non-adherence

BP readings will be automatically uploaded from the subject's smartphone to the Way to Health platform. If the subject goes 7 days without a single BP measurement, Way to Health will alert study personnel. Study personnel will contact the subject by phone to remind them to check their BP and troubleshoot any potential technical

problems. If the subject indicated that they do not wish to continue BP monitoring, study alerts will be discontinued and the study team will setup a time for the subject to return the BP device. Even if the subject completely stops monitoring their BP, they will still remain in the study and be encouraged to complete the 30 and 90-day follow-up assessments. For analysis, if a subject completely stops BP monitoring, they will remain in the final analytic dataset but be considered “non-adherent” for the remaining study days (further details in section 8).

7.2 48 Hour Follow-up Phone Call

Enrolled subjects will be contacted at 48 hours +/- 24 hours after enrollment. The purpose of this call will be to ensure the subject is able to properly use the device. We will ask subjects if they have had any difficulty using the Withings blood pressure monitor or interacting with Way to Health. If the patient is having difficulty using either system, troubleshooting will occur via the telephone. If the issue cannot be resolved, the subject will be offered an additional in-person visit to trouble shoot the device and/or repeat device training. The subject will also be screened for adverse events during this telephone call.

7.3 30 Day Interview

Enrolled subjects will be contacted at 30 days +/- 3 days after enrollment via electronic messaging (text message and/or email). The subject will be asked to log into Way to Health and complete a short form. This form will screen for adverse events and collect 30 day outcome data. Blood pressure readings and adherence to twice daily blood pressure monitoring will be collected automatically via Way to Health and will not need to be assessed over the telephone. Secondary outcomes assessed will include:

- TIA or stroke since enrollment
- Number of physician visits since enrollment (Primary care, cardiology, other)
- Number of emergency department visits since enrollment and reason for each visit
- Number of changes in antihypertensive medications since enrollment (dose adjustment and/or addition of a new agent)
- Patients perception of blood pressure monitoring device and study protocol ease of use (very difficult, moderately difficult, mildly difficult, easy to use)
- Patients perception of the utility of blood pressure monitoring (very useful, moderately useful, mildly useful, not useful)
- Patients perception of blood pressure control (adequately controlled, not adequately controlled)

Subjects who do not complete the online form will be contacted by telephone in order to assess the same information.

7.4 90 Day Follow-up Visit

At 90 +/- 7 days from enrollment the subject will be seen for an in-person visit. They will be asked to return the blood pressure monitor at that time and be screened for adverse events. Outcomes will again be assessed. Blood pressure readings and adherence to twice daily blood pressure monitoring will be collected automatically via Way to Health and will not need to be assessed during this in-person visit. Secondary outcomes assessed will include:

- TIA or stroke since 30 day phone call
- Number of physician visits since 30 day phone call (Primary care, cardiology, other)
- Number of emergency department visits since 30 day phone call and reason for each visit
- Number of changes in antihypertensive medications since 30 day phone call (dose adjustment and/or addition of a new agent)
- Patients perception of blood pressure monitoring device and study protocol ease of use (very difficult, moderately difficult, mildly difficult, easy to use)

- Patients perception of the utility of blood pressure monitoring (very useful, moderately useful, mildly useful, not useful)
- Patients perception of blood pressure control (adequately controlled, not adequately controlled)

Heart rate and blood pressure will be assessed in the non-dominant arm using an automated cuff. This will be repeated 3 times and averaged to determine final blood pressure. The modified Rankin Scale and NIHSS will also be assessed, as described in section 7.1. Research personnel assessing both the mRS and the NIHSS will be trained and certified in its use. Finally, for each subject we will tabulate the number of telephone calls to the study team initiated by the subject and the purpose of the call (blood pressure reading high/low, technical difficulty with device, other).

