4.3 Inclusion Criteria

1. Adult, age ≥ 18 years
2. History of ischemic stroke, intraparenchymal hemorrhage, or high risk TIA (defined by ABCD2 ≥ 4) with the past 5 years prior to enrollment
3. Hypertensive at time of screening, defined by SBP >140 mm Hg or DBP >90 mm Hg
4. Enrollment must occur within 30 days of study screening
5. Must own a smart phone capable of interacting with the connected blood pressure cuff (Apple iPhone 3GS or higher; Android 4.0 or higher with Bluetooth connectivity)
6. Must be able to identify at least one adult (≥ 18) with internet access and/or a smart phone with text messaging capability who could serve as a social support person.
7. Willingness and ability to sign informed consent by patient

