We will compare secondary outcomes across study arms including number of calls to the study team, number of physician visits, number of emergency department visits, number of changes in antihypertensive medications, and the patient perception of: study protocol, utility of blood pressure monitoring, and blood pressure control. We will also determine the relationship between adherence to blood pressure monitoring and change in blood pressure during the study period. For this analysis, we will first determine the average adherence in the study population. We will compare the change in blood pressure in those with above average adherence to those with below average adherence. This will be done in the full study population and then stratified by study arm. In an exploratory analysis multivariable regression will be utilized to determine which factors were associated with a high level of adherence to the study protocol, defined as adherence above the study median. We will investigate the following variables in a univariate analysis: age, sex, race, ethnicity, income, social support in the home, employment status, MMSE score, NIHSS, and modified Rankin Scale. Variables in the univariate analysis with $p < 0.10$ will be incorporated into a multivariable logistic regression model. We will test for an interaction between the social incentive and the variables in the multivariable model.

9. Data Handling and Record Keeping

9.1 Confidentiality.

- Paper-based records will be kept in a secure location and only be accessible to personnel involved in the study.
- Computer-based files will only be made available to personnel involved in the study through the use of access privileges and passwords.
- Prior to access to any study-related information, personnel will be required to sign statements agreeing to protect the security and confidentiality of identifiable information.
- Whenever feasible, identifiers will be removed from study-related information.

- A Certificate of Confidentiality will be obtained, because the research could place the subject at risk of criminal or civil liability or cause damage to the subject's financial standing, employability, or liability.
- A waiver of documentation of consent is being requested, because the only link between the subject and the study would be the consent document and the primary risk is a breach of confidentiality. (This is not an option for FDA-regulated research.)

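### Employment status in section 7.1 has no level for eligible adults who are unemployed, homemakers or students, yet section 8 tests it as a predictor of high adherence

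*Combined protocol and SAP*

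**What the plan says.** Section 7.1 lists the data taken at enrollment. For employment it gives "employment status (currently employed, disabled, retired", three levels with no residual. Other lists in the same paragraph are closed off: past medical history ends with an 'other' entry, insurance status includes 'none', and stroke etiology has a residual level.

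Section 4.3 sets the age criterion as "Adult, age ≥ 18 years". Neither 4.3 nor the exclusions in 4.4 mention employment.

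Section 8 returns to the variable: "In an exploratory analysis multivariable regression will be utilized to determine which factors were associated with a high level of adherence", with high meaning above the study median. The ten candidates are "age, sex, race, ethnicity, income, social support in the home, employment status, MMSE score, NIHSS, and modified Rankin Scale". Each is tested univariately, those with p < 0.10 enter a multivariable logistic model, and interactions with the social incentive are then tested. The section gives no rule for a missing covariate. The analysis answers the part of the secondary objective (section 1.2) about individual factors related to adherence.

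**The concern.** A categorical predictor is usable only if every eligible subject has a correct level. Here a subject who does not work, is not disabled and is not retired has none. Staff completing the form must either choose a level that is untrue or leave the item empty.

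Employment is a plausible predictor in this trial, because readings are due in fixed morning and late-afternoon-to-evening windows (section 7.1), and a working day may help or hinder keeping to them. Mixing people without jobs into the disabled or retired group changes what the employment contrast measures. It can also change whether employment passes the p < 0.10 screen. What is at stake is one candidate in an exploratory analysis.

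**Working it through.** The plan states no figure on this point, so there is none to reproduce. The check has two parts.

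**1. Text comparison**

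- Who may enter: adults of 18 or over meeting 4.3 and 4.4, with no employment condition.
- What can be recorded: three employment levels (7.1).
- What is analyzed: employment status, as one of ten candidates (section 8).

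The recordable levels do not cover the eligible population, and the variable is used in a planned analysis.

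**2. Possible size**

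Only the total of 90 subjects (section 4.2) comes from the documents. They give no unemployment rate, no count of disabled subjects and no adherence by employment, so the rest is assumed.

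*Number affected.* If 5% to 20% of subjects had no valid level, that is 0.05 × 90 = 4.5 to 0.20 × 90 = 18, or about 5 to 18. If all were left blank, about 72 to 85 would have a usable value.

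*Effect of miscoding.* Assume 25 subjects are coded disabled, of whom 16 are disabled and 9 (10% of 90) are unemployed. Assume high adherence in 60% of the employed and 30% of the disabled.

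- True odds ratio, disabled versus employed: (0.30/0.70) / (0.60/0.40) = 0.429/1.5 = 0.286.
- Proportion in the mixed group: p = (16 × 0.30 + 9 × u)/25, where u is high adherence among the unemployed.
- Estimated odds ratio: [p/(1 − p)]/1.5.

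| u | p | Estimated OR | Change in log OR |
|---|---|---|---|
| 0.60 (like the employed) | 10.2/25 = 0.408 | 0.459 | 38% smaller |
| 0.30 (like the disabled) | 7.5/25 = 0.300 | 0.286 | none |
| 0.15 | 6.15/25 = 0.246 | 0.218 | 22% larger |

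The last column compares ln(OR) with ln(0.286) = −1.253: ln(0.459) = −0.778, and 0.778/1.253 = 0.62; ln(0.218) = −1.525, and 1.525/1.253 = 1.22.

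With u held at 0.60 and the number misplaced varied within the 25, 5 misplaced gives an OR of 0.375 (22% smaller on the log scale) and 13 misplaced gives 0.559 (54% smaller).

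If the 9 are coded retired instead, the disabled-versus-employed odds ratio is untouched and the retired contrast takes the distortion.

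*Against sampling error.* In the u = 0.60 case the log odds ratio shifts by 1.253 − 0.778 = 0.475. The 16 truly disabled subjects alone contribute a standard error of √(1/4.8 + 1/11.2) = 0.55, before the employed group is added.

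**The case against.** The strongest reply is that section 7.1 is a narrative list. Section 9.3 makes the case report form the primary data collection instrument; that form is not in the documents and may already carry a fuller set of levels. This stands as a limit on what can be concluded, but it does not rescue the text: the protocol states three levels, and anyone building or checking the form from it would use three.

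A second reply is that the consequence is small. This also stands. The analysis is labeled exploratory, and the illustrative shift is no larger than the sampling error from the disabled group alone.

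A reader might draw three stronger conclusions that the documents do not support.

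- *The bias is toward no effect.* That follows only if the unemployed adhere more like the employed and are coded disabled. The table shows that other assumptions give no bias or an exaggerated effect.
- *Subjects left blank are lost from the multivariable model.* They are lost from the univariate test of employment. They are lost from the multivariable model only if employment passes p < 0.10 and incomplete records are dropped.
- *Hemorrhage and TIA cannot be classified either.* Section 4.3 admits "History of ischemic stroke, intraparenchymal hemorrhage, or high risk TIA", and 7.1 lists "etiology of stroke (large vessel disease, small vessel disease, cardioembolic, other defined etiology, cryptogenic". The levels 'other defined etiology' and 'cryptogenic' can take a hemorrhage, and a TIA can be given a vascular mechanism. Neither etiology nor event type is among the section 8 predictors. The list in 7.1 shows no field for the type of qualifying event, but eligibility is confirmed at enrollment (7.5) and necessary source data go onto the case report form (9.2), so the event may already be recorded there.

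**Conclusion.** The point holds for employment status and is minor. As written, section 7.1 gives some eligible adults no valid level for a variable that section 8 analyzes, so the employment result would be distorted in an unknown direction or rest on fewer subjects. In the illustration, a true odds ratio of 0.29 is estimated anywhere from 0.22 to 0.46, depending on how the 9 misplaced subjects adhere. Apart from the total of 90, every input to that range is an assumption, including that all 9 are coded disabled. The primary adherence comparison and the sample size do not depend on this variable.

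**What to change.** In section 7.1, add a fourth employment level, 'not employed / other (unemployed, homemaker, student)', and make the case report form match. In section 8, state that the four-level variable is used in the predictor analysis and that a sparse level will be collapsed, with the rule for collapsing written down beforehand.

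The cost is one answer option on the enrollment form. The downside is one more, possibly sparse, category in an exploratory model of at most 90 subjects. Collapsing deals with that at analysis, whereas a level never collected cannot be rebuilt from the listed data. The change is best made before enrollment, since subjects already coded might have to be asked again.

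A field for type of qualifying event (ischemic stroke, intraparenchymal hemorrhage, TIA) is optional. It would help the baseline description only. The etiology levels need no change on this account.
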